7.7. Concomitant Therapy

All concomitant medication taken during the study must be recorded on the Concomitant Medication electronic case report form (eCRF).

Patients will be instructed to consult the investigator or other appropriate study personnel at the site before taking any new medications or supplements during the study.

Additional drugs are to be avoided unless required to treat AEs or for the treatment of an ongoing medical condition. If the need for other concomitant medications arises, discontinuation of the patient from the investigational product or the study will be at the discretion of the investigator in consultation with Lilly or its designee (Section 8.2).

Treatment with concomitant therapies during the study is permitted only as described below and in [Table JAHW.7](#). During Part A, the dosages of concomitant treatment may only be adjusted for safety reasons, with the exception of topical corticosteroid eye drops.

Methotrexate, mycophenolate mofetil, and csDMARDs:

- Chronic stable use of MTX is permitted up to a maximum dose of 25 mg/m²/week throughout the study.
- Patients must be on a stable dose of MTX for at least 4 weeks prior to screening, and remain on the same dose throughout Part A.
- During Part B, MTX may be initiated or the dose increased, decreased, or discontinued, at the discretion of the investigator, and according to local clinical practice.
- Local standard of care should be followed for concomitant administration of folic acid.
- Chronic stable use of csDMARDs (other than MTX) and mycophenolate mofetil is permitted. Patients must be on a stable dose for at least 4 weeks prior to screening.
- During Part A, initiation of new csDMARDs and/or increases in dose are not permitted.
- During Part B, other csDMARDs or mycophenolate mofetil may be initiated, or the dose increased, decreased, or discontinued, at the discretion of the investigator, and according to local clinical practice.
- Concomitant use of >2 csDMARDs (including MTX) is not allowed.

Topical steroid eye drops:

- Topical steroid eye drops, with a maximum of 4 drops/day per eye at screening, are permitted as background therapy during the study. The dose must have been stable for at least 2 weeks prior to screening.
- Steroid drop tapering is recommended as shown in the following table:

Study Interval	Dose Reduction
Week 0–Week 4	No dose changes permitted
Week 4–Week 8	Reduce drops to a maximum of 3 drops/day per eye

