Week 8–Week 20	Reduce drops to a maximum of 2 drops/day per eye
Week 20–Week 24	No dose changes permitted
Week 24 onward (Part B)	Reduce drops at the discretion of the treating clinician to any dose, including zero

- If tapering is not tolerated during Part A or Part B, the number of drops can be increased up to the number received at screening.
- The topical steroid eye drop formulation (Maxidex, Predforte, or equivalent) should remain the same as that used at screening and will not change for individual patients throughout Part A, unless required for safety or supply issues; the formulation may be changed during Part B.

Oral corticosteroids:

- Chronic stable use of oral corticosteroids is permitted and defined as daily doses of ≤10 mg/day or 0.2 mg/kg/day prednisone equivalent, whichever is less.
- Patients must be on a stable dose for at least 2 weeks prior to screening and 4 weeks prior to baseline, and remain on the same dose throughout Part A, except for treatment of an AE.

- During Part B, oral corticosteroids may be initiated, or the dose increased, decreased, or discontinued, at the discretion of the investigator.

Intra-articular corticosteroid joint injections:

- A maximum of 8 injections are permitted per year.
- No more than 2 injections are permitted in a single session.
- No injections are permitted within 4 weeks prior to Visit 2.

Intraocular corticosteroid injections:

- Depot peri-ocular, peri-ocular or intraocular corticosteroid injections are not permitted within 30 days prior to Visit 2 or during Part A.
- Intraocular or peri-ocular corticosteroid injections are permitted during Part B at the discretion of the investigator.

Other corticosteroids

- With the exception of oral and intra-articular corticosteroids, patients should not receive other systemic corticosteroids during Part A, including intramuscular corticosteroids.
- During Part B, other systemic steroids may be administered; however, the daily dose should be ≤ 10 mg/day or 0.2 mg/kg/day prednisone equivalent, whichever is less.
- Topical, intranasal, and inhaled corticosteroids are permitted.

Analgesics and NSAIDs

- Chronic stable use of NSAIDs and analgesics is permitted. Patients must be on a stable dose for at least 1 week prior to Visit 2.
- Increases in dose and/or introduction of new NSAIDs and analgesics are not permitted during Part A, except for treatment of an AE.

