9.1.2.3. PediACR30/50/70/90/100 Assessments

The PediACR30 consists of the 6 core criteria listed below. The definition of improvement is at least 30% improvement from baseline in 3 of any 6 variables in the core set, with no more than 1 of the remaining variables worsening by >30%.

- Number of active joints (defined as a joint that is swollen or in the absence of swelling has loss of passive motion accompanied by either pain on motion or joint tenderness) in 73 joints
- Number of joints with limited range of motion in 69 joints

- Physician's Global Assessment of Disease Activity (21-circle visual analogue scale [VAS]) (Section 9.1.2.4)
- Parent's Global Assessment of Well-Being (Section 9.1.3)
- Physical function as assessed by the Childhood Health Assessment Questionnaire (CHAQ) (Section 9.1.3)
- Acute-phase reactant (high-sensitivity C-reactive protein [hsCRP] and erythrocyte sedimentation rate [ESR])

PediACR50/70/90/100 responses are efficacy measures that are calculated as improvements of at least 50%, 70%, 90% and 100%, respectively, in the PediACR Core Set values listed above.

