6.3.1.1. Nonresponder Imputation (NRI)

An NRI imputation method can be justified based on the composite strategy (ICH E9R1) for handling intercurrent events. In a composite strategy with NRI, a patient is defined as a responder only if

- (i) they meet the clinical requirements for response at the predefined time, and
- (ii) they remain on the assigned study treatment;

failing either criteria by definition (i) or (ii) makes them a nonresponder.

Binary efficacy and health-outcome variables, excluding the primary outcome variable, will be imputed using NRI. Patients will be considered a nonresponder for the NRI analysis if they do not meet the clinical response criteria or are entirely missing the visit at the analysis time point. Patients without at least 1 postbaseline observation will also be defined as nonresponders for the NRI analysis.

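### Steroid-injected joints have no scoring rule in the Part A PediACR analysis, so an injected joint that settles counts as improvement in two of the six core items

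*Protocol*

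**What the plan says.** Protocol 7.7 gives three conditions for intra-articular injections. The yearly limit reads "A maximum of 8 injections are permitted per year". One session may include two at most, and the four weeks leading up to Visit 2 must be free of them. Table JAHW.7 repeats these conditions in the column that lists conditions for use in Part A. The same section exempts this route from the Part A steroid restriction: "With the exception of oral and intra-articular corticosteroids, patients should not receive other systemic corticosteroids during Part A". The next row of Table JAHW.7, on intraocular injections, rules them out for Part A; the intra-articular row does not.

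Two other statements sit awkwardly with this permission. Section 7.7 opens with a general rule: "During Part A, the dosages of concomitant treatment may only be adjusted for safety reasons, with the exception of topical corticosteroid eye drops". Table JAHW.7 also enters No for intra-articular injections under both as-needed and chronic use, and then gives conditions for their use.

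PediACR 30/50/70/90/100 is a Part A secondary endpoint for patients with JIA-associated uveitis. Protocol 9.1.2.3 defines PediACR30 as "at least 30% improvement from baseline in 3 of any 6 variables in the core set", with a limit on worsening in the other items. Two of the six items are joint counts: active joints out of 73, and joints with limited motion out of 69. Neither that section nor SAP Table JAHW.7.1 mentions injected joints.

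Under SAP 6.3.1.1, patients are nonresponders if they "do not meet the clinical response criteria or are entirely missing the visit at the analysis time point", and response also requires staying on assigned treatment. SAP 6.9 names intra-articular injections only as a drug class that may appear in concomitant-medication summaries.

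**The concern.** A steroid injection acts on the joint that receives it. If that joint is quiet at Week 24, the plan as written scores it as improved in both joint counts, and the improvement is reported under baricitinib or adalimumab. The study is open-label, so whoever decides when to inject knows the assigned drug.

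Other background treatment that could move an endpoint is held more tightly. Eye-drop doses are frozen from Week 20 to Week 24, and methotrexate, other csDMARDs and oral steroids are kept stable through Part A. Intra-articular injection has no quiet period before Week 24.

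SAP 6.3 describes intercurrent events as including those that change how a variable should be read. An injection into a counted joint fits that description, yet it is assigned no strategy. At stake is an upward bias in the Part A PediACR rates, in arms small enough for one child to be visible.

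**Working it through.** The documents give no PediACR rate, power or sample size, so there is no plan figure to reproduce. The check applies the stated response rule directly.

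**Inputs.** Two injections per session, eight per year, and no separate Part A cap (Protocol 7.7). Response needs three of six items improved by the threshold percentage, with at most one of the rest worse by more than 30% (Protocol 9.1.2.3).

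**Assumptions, not in the documents.** Each injected joint is both active and limited at baseline and is neither at the analysis visit. The same N joints are affected in both counts. No other joint changes.

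**Step 1: effect on the joint counts.** If k injected joints settle out of N, each count improves by 100 × k / N percent. With k = 2:

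| N affected joints | Improvement in each count | Highest threshold reached by both counts |
|---|---|---|
| 2 | 100% | 100 |
| 3 | 66.7% | 50 |
| 4 | 50% | 50 |
| 5 | 40% | 30 |
| 6 | 33.3% | 30 |
| 7 | 28.6% | none |

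Both counts therefore reach 30% for N = 2 to 6, 50% for N = 2 to 4, and 70% or more only for N = 2.

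**Step 2: the three-of-six rule.** The two counts supply two items. With the other four unchanged, 2 < 3 and the child is a nonresponder at every N. If one further item (physician's global, parent's global, CHAQ function or acute-phase reactant) improves by 30%, the total is 3 of 6. The child is then a PediACR30 responder for N = 2 to 6, provided the worsening limit is met.

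**Step 3: several sessions.** Nothing prevents all eight yearly injections, in four sessions of two, from falling within the 24 weeks. With k = 8, the 30% threshold is met up to N = 26 (8/26 = 30.8%; 8/27 = 29.6%).

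**Step 4: with injected joints held at their pre-injection status.** Take the Step 2 child, with both joints still active and limited at the last visit before injection. Each count improves by 0%, only the third item remains improved, and 1 of 6 gives a nonresponder.

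**Step 5: weight of one child.** If every evaluable patient were assessed for PediACR, one child would be 1/20 = 5 percentage points at the minimum baricitinib number, 1/30 = 3.3 points at 30 patients, and 1/4 = 25 points at the minimum adalimumab number. The actual denominators are unknown: the endpoint covers only JIA-associated uveitis, and SAP Table JAHW.7.1 divides by the number assessed.

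**The case against.** A reader might infer that injecting two joints is enough to make a child a responder with no drug effect at all, even up to PediACR100. The documents do not support that. Two injections act directly on two of six items, and a third must improve as well. PediACR100 by this route needs exactly two affected joints, full resolution of both, and a third item improved by 100%. If that item were the physician's global, it would have to fall to 0, meaning no activity. Protocol 9.1.2.4 does not limit that rating to arthritis, and every child enters with active uveitis. A global of 0 is hard to reconcile with an absent drug effect.

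A reader might also take 5 and 25 points as the size of the bias. They are only the weight of one child under assumed denominators, and hold for any event in arms that small. The documents give no injection rate and no baseline joint counts, and entry requires no active joints.

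The strongest point against the concern is its limited reach. PediACR is one of many descriptive secondary endpoints, and both documents say no treatment comparison will be made. That stands and caps the importance. It does not supply the missing scoring rule.

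On the apparent contradictions, the general Part A rule concerns dosages, and section 7.7 gives injections their own conditions. The double No need not mean prohibited, since the intraocular row carries the same entries and is then permitted in Part B. These are fair readings, but sites could read the text differently, so reconciliation is still needed.

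Finally, treating an injection as permitted background therapy is a legitimate estimand choice. If that is intended, the SAP should say so; at present it makes no choice.

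**Conclusion.** The gap is real and modest. Injections are allowed in Part A up to the Week 24 visit, and no rule governs how injected joints enter PediACR. As written, the scoring can only favour response. Two settled joints carry both joint-count items past 30% in a child with 2 to 6 affected joints, and one further improved item completes PediACR30, subject to the worsening limit. That third improvement is plausible in a child with few affected joints, because the global ratings and CHAQ function may follow the treated joints.

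The result rests on the injected joints being both active and limited at baseline and settling by the visit. How often this would happen cannot be estimated from the documents. The primary endpoint, the futility rules and the success rule use anterior chamber cells only and are not affected. It is worth correcting before the Part A PediACR analysis, but it does not bear on whether the study is declared positive.

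**What to change.** In the PediACR row of SAP Table JAHW.7.1, state that a joint injected with steroid after baseline keeps its last pre-injection active and limited-motion status at all later Part A visits. If the records do not identify which joint was injected, add a sensitivity analysis that counts any patient injected in Part A as a PediACR nonresponder. List the patients and joints injected in Part A by arm.

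A rule making every patient injected within a fixed window before the visit a nonresponder is not recommended for the main analysis. It would override improvement in joints that were never injected, and it is a debatable estimand choice.

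Separately, reconcile the general Part A rule in Protocol 7.7, the injection bullets and the two No entries in Table JAHW.7. This review takes no view on which should govern care.

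The cost is SAP wording and a flag built from concomitant-medication and joint-assessment data. Concomitant medication is already recorded on the eCRF, and joints are assessed at every scheduled Part A visit. Whether the record names the injected joint is not stated and should be checked first. The PediACR rate will be slightly lower where injections occurred, since a joint that would have settled on study drug anyway stays counted as affected. Holding joint status does not remove any knock-on effect of an injection on the global ratings or CHAQ function.

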7.8. Treatment after the End of the Study

7.8.1. Treatment after Study Completion

After the conclusion of the study, continued access to baricitinib will not be provided.

7.8.2. Special Treatment Considerations

Patients receiving baricitinib who experience a treatment failure after at least 24 weeks of treatment can have concomitant medication altered (as described in Section 7.7), but should also be considered for discontinuation from the study (see Section 8.2).

Treatment failure is defined by the presence of 1 or more of the following:

- A 2-step increase in SUN cell-activity score (anterior chamber cells) over 2 consecutive readings for patients with a baseline grade of 1+ or 2+.
- Sustained non-improvement in SUN cell-activity score for 2 consecutive readings for patients with a baseline grade of 3+ or greater.
- Only partial improvement of other ocular co-morbidity for 2 consecutive assessments.
 - Ocular co-morbidities are defined as:
 - Disc swelling and/or cystoid macular edema, as gauged clinically and confirmed by optical coherence tomography (OCT) evidence
 - Sustained raised intraocular pressure (>25 mm Hg) for more than 1 month, not responding to topical anti-hypertensives
 - Sustained hypotony (<6 mm Hg) for more than 1 month
 - Reduction in vision (LogMAR test) of 15 letters, secondary to active uveitis (excluding cataract)
 - **Note:** Patients can remain in the study in the event of cataract.
- No improvement in SUN cell-activity score over 2 consecutive readings after 6 months of therapy.
- Worsening of existing (on enrollment) ocular co-morbidity (as defined above) after 12 weeks of therapy.

8. Discontinuation Criteria

8.1. Discontinuation from Study Treatment

8.1.1. *Temporary Interruption of Investigational Product*

In some circumstances, patients may need to temporarily interrupt treatment as a result of AEs or abnormal laboratory values that may have an unclear relationship to investigational product.

Except in cases of emergency, it is recommended that the investigator consult with Lilly (or its designee) before temporarily interrupting therapy for reasons other than those defined in [Table JAHW.8](#).

For the abnormal laboratory findings and clinical events (regardless of relatedness) listed in [Table JAHW.8](#), specific guidance is provided for temporarily interrupting treatment and when treatment may be restarted. Retest frequency and timing of follow-up laboratory tests to monitor the abnormal finding is at the discretion of the investigator. Investigational product that was temporarily interrupted because of an AE or abnormal laboratory value not specifically covered in [Table JAHW.8](#) may be restarted at the discretion of the investigator.

Table JAHW.8. Criteria for Temporary Interruption of Investigational Product

Hold Investigational Product if the Following Laboratory Test Results or Clinical Events Occur:	Investigational Product May be Resumed When:
WBC count <2000 cells/ μ L (<2.00 x 10 ³ / μ L or <2.00 billion/L)	WBC count \geq 3000 cells/ μ L (\geq 3.00 x 10 ³ / μ L or \geq 3.00 billion/L)
ANC <1000 cells/ μ L (<1.00 x 10 ³ / μ L or <1.00 billion/L)	ANC \geq 1500 cells/ μ L (\geq 1.50 x 10 ³ / μ L or \geq 1.50 billion/L)
Lymphocyte count <500 cells/ μ L (<0.50 x 10 ³ / μ L or <0.50 billion/L)	Lymphocyte count \geq 1000 cells/ μ L (\geq 1.00 x 10 ³ / μ L or \geq 1.00 billion/L)
Platelet count <75,000/ μ L (<75 x 10 ³ / μ L or <75 billion/L)	Platelet count \geq 100,000/ μ L (\geq 100 x 10 ³ / μ L or \geq 100 billion/L)
eGFR <40 mL/min/1.73 m ² (from serum creatinine) for patients with screening eGFR \geq 60 mL/min/1.73 m ²	eGFR \geq 50 mL/min/1.73 m ²
eGFR <30 mL/min/1.73 m ² (from serum creatinine) for patients with screening eGFR \geq 40 to <60 mL/min/1.73 m ²	eGFR \geq 40 mL/min/1.73 m ²
ALT or AST >5 x ULN	ALT and AST return to <2 x ULN, and IP is not considered to be the cause of enzyme elevation
Hemoglobin <8 g/dL (<80.0 g/L)	Hemoglobin \geq 10 g/dL (\geq 100.0 g/L)
Symptomatic herpes zoster	All skin lesions have crusted and are resolving
Infection that, in the opinion of the investigator, merits the IP being interrupted	Resolution of infection that, in the opinion of the investigator, merits the IP being restarted

Abbreviations: ALT = alanine aminotransferase; ANC = absolute neutrophil count; AST = aspartate aminotransferase; eGFR = estimated glomerular filtration rate; IP = investigational product; ULN = upper limit of normal; WBC = white blood cell.

8.1.2. Permanent Discontinuation from Investigational Product

Investigational product must be permanently discontinued if the patient or the patient's designee requests to discontinue investigational product.

Discontinuation of the investigational product for abnormal liver tests should be considered by the investigator after consultation with the Lilly-designated medical monitor when a patient meets 1 of the following conditions:

- ALT or AST $>8 \times$ ULN
- ALT or AST $>5 \times$ ULN for more than 2 weeks after temporary interruption of investigational product
- ALT or AST $>3 \times$ ULN and TBL $>2 \times$ ULN or international normalized ratio (INR) >1.5
- ALT or AST $>3 \times$ ULN with the appearance of fatigue, nausea, vomiting, right upper-quadrant pain or tenderness, fever, rash, and/or eosinophilia ($>5\%$)
- ALP $>3 \times$ ULN that is deemed to be of liver origin and drug-related
- ALP $>2.5 \times$ ULN and TBL $>2 \times$ ULN
- ALP $>2.5 \times$ ULN with the appearance of fatigue, nausea, vomiting, right upper-quadrant pain or tenderness, fever, rash, and/or eosinophilia ($>5\%$)

Note: Patients who are discontinued from investigational product due to a hepatic event or liver test abnormality should have additional hepatic safety data collected via the hepatic safety eCRF.

Investigational product should be permanently discontinued if any of the following laboratory abnormalities are observed:

- White blood cell count $<1000 \text{ cells}/\mu\text{L}$ ($1.00 \times 10^3/\mu\text{L}$ or $1.00 \text{ billion}/\text{L}$)
- ANC $<500 \text{ cells}/\mu\text{L}$ ($0.50 \times 10^3/\mu\text{L}$ or $0.50 \text{ billion}/\text{L}$)
- Lymphocyte count $<200 \text{ cells}/\mu\text{L}$ ($0.20 \times 10^3/\mu\text{L}$ or $0.20 \text{ billion}/\text{L}$)
- Hemoglobin $<6.5 \text{ g/dL}$ ($<65.0 \text{ g/L}$)

Note: Temporary interruption rules (see Section 8.1.1) must be followed where applicable. For laboratory values that meet permanent discontinuation thresholds, investigational product should be discontinued. However, if in the opinion of the investigator the laboratory abnormality is due to intercurrent illness such as cholelithiasis or another identified factor, laboratory tests may be repeated. Only when the laboratory value meets resumption thresholds (Table JAHW.8) following the resolution of the intercurrent illness or other identified factor may the investigator restart investigational product after consultation with the Lilly-designated medical monitor.

Use of analgesics “as needed” must lead to a thorough diagnostic assessment of all potential underlying causes and, if lack of efficacy cannot be ruled out, to considering permanent discontinuation of the investigational product.

In addition, patients will be discontinued from investigational product in the following circumstances:

- Pregnancy
- Malignancy
- HBV DNA detected with a value above the limit of quantitation (see Section 9.4.4)
- Development of a VTE (DVT/PE) during the study

Patients discontinuing from the investigational product prematurely for any reason should complete follow-up per Section 2 (Schedule of Activities), Section 9.2 (Adverse Events), and Section 9.4 (Safety).

